2.2. Part B (Cohorts 1 and 3; Multiple-Ascending Doses)

Procedure	Screening	Days										FU ^a	ED ^b	Comments
		-1	1	2	3 to 6	7	8	9 to 13	14	15 to 17	28			
Informed Consent	X													
Admission to CRU ^c		X												
Discharge from CRU											Day 17			
LY3478045 Administration						X								
Medical History	X													Information regarding occasional use of vitamin/mineral supplements will be taken as a part of the medical history evaluation at the time of subject screening.
Complete Physical Examination	X											X	X	Targeted PE may be conducted at other visits at the discretion of the investigator.
Height	X													
Weight	X	X									Day 15	X	X	
Pregnancy Test	X	X										X	X	Serum pregnancy test will be performed at screening and urine pregnancy test will be performed at all other specified

	Screening	Days										FU ^a	ED ^b	Comments
Procedure	≤28 days before Day -1	-1	1	2	3 to 6	7	8	9 to 13	14	15 to 17	28			
														timepoints.
Blood Pressure and Pulse Rate (Supine) ^c	X	X	P, every 1 h up to 12 h postdose	24, 36 h	48, 72 h				X		X	X		
Body Temperature	X	X										X	X	
Clinical Laboratory Tests (See Appendix 2)	X	X	P		Day 4	X			X		X	X		
Serum Creatinine			X			X			X					
Total Testosterone, Follicle-Stimulating Hormone, and Luteinizing Hormone	X		P	P							X	X	Samples will be collected early in the morning on Days 1 and 2, at the same time for both days, before or immediately after breakfast.	
Single 12-Lead ECG	X										X	X		
TriPLICATE 12-Lead ECG			Predose: 1.5 h, 1 h, and 30 min.						P, 0.5, 1.5, 2.5, 4, 6, 8, 12, 16 h	24 h				
Adverse Event Recording	X	X	X	X	X	X	X	X	X	X	X	X		
Pharmacokinetic Sampling ^d			P, 0.75, 1.5, 3, 4, 6, 8, 12, 16 h	24 h (predose)		P			P, 0.75, 1.5, 3, 4, 6, 8, 12, 16 h	24, 48, 72 h			Sampling times may be adjusted based upon review of interim PK	
Fasting Insulin and Adiponectin			P						P					
Meal (Low Fructose)			20 min, 6 h, 12 h						20 min, 6 h, 12 h					

Procedure	Screening ≤28 days before Day -1	Days										FU ^a	ED ^b	Comments
		-1	1	2	3 to 6	7	8	9 to 13	14	15 to 17	28			
Fructose Beverage (for Fructose Tolerance Test)			during meal: 20 min, 6, 12 h						during meal: 20 min, 6, 12 h					
Fructose Tolerance Test Assay ^d			CCI	CCI					CCI	CCI				
Genetic Sample		P												
Fasting Biomarker Samples (Nonpharmacogenetic)		X		X							Day 15			

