2.3. Part B (Cohorts 2 and 4; Multiple-Ascending Doses)

Procedure	Screening ≤28 days before Day -3	Days												FU ^a	ED ^b	Comments
		-3	-2	-1	1	2	3 to 6	7	8	9 to 13	14	15, 16, 17				
Informed Consent	X															
Admission to CRU ^c		X														
Discharge from CRU													Day 17			
LY3478045 Administration							X									
Medical History	X														Information regarding occasional use of vitamin/mineral supplements will be taken as a part of the medical history evaluation at the time of subject screening.	
Complete Physical Examination	X													X	X	Targeted PE may be conducted at other visits at the discretion of the investigator.
Height	X															
Weight	X	X											Day 15	X	X	
Pregnancy Test	X	X												X	X	Serum pregnancy test will be performed at screening and urine pregnancy test will be performed at all other specified timepoints.
Blood Pressure and Pulse Rate (Supine) ^c	X			X	P, every 1 h up to 12 h postdose	24, 36 h	48, 72 h						X		X	
Body Temperature	X			X										X	X	
Clinical Laboratory Tests (See Appendix 2)	X	X			P		Day 4	X					X		X	
Total Testosterone, Follicle-Stimulating Hormone, and Luteinizing Hormone	X				P	P								X	X	Samples will be collected early in the morning on Days 1 and 2, at the same time for both days, before or immediately

	Screening	Days											FU ^a	ED ^b	Comments
Procedure	≤28 days before Day -3	-3	-2	-1	1	2	3 to 6	7	8	9 to 13	14	15, 16, 17	28		
															after breakfast.
Serum Creatinine					X			X			X				
Single 12-Lead ECG	X											X	X		
TriPLICATE 12-Lead ECG					Predose: 1.5 h, 1 h, and 30 min.						P, 0.5, 1.5, 2.5, 4, 6, 8, 12, 16 h	24 h			
Adverse Event Recording	X	X	X	X	X	X	X	X	X	X	X	X	X		
Pharmacokinetic Sampling ^d					P, 0.75, 1.5, 3, 4, 6, 8, 12, 16 h	24 h (predose)		P, 0.75, 1.5, 3, 4, 6, 8, 12, 16 h	24 h (predose)		P, 0.75, 1.5, 3, 4, 6, 8, 12, 16 h	24, 48, 72 h		Sampling times may be adjusted based upon review of interim PK	
Fasting insulin and Adiponectin					P						P				
Meal (Low Fructose)			breakfast		20 min, 6, 12 h			20 min			20 min, 6, 12 h				
Fructose Beverage (for Fructose Tolerance Test)					during meal: 20 min, 6, 12 h						during meal: 20 min, 6, 12 h				
Fructose Tolerance Test Assay ^d					CCl	24 h (predose and premeal)					CCl	CCl			
CCl				X				X							Atorvastatin will be administered 4 hours after LY3478045 administration on Day 7 or 4 hours after breakfast on Day -2.

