5.1.2. Part B

Part B will be initiated after assessing safety, tolerability, PK, and PD data through Cohort 3 in Part A.

[figure not shown]
Multiple-ascending oral doses of LY3478045 will be administered once daily for 14 days in up to 4 cohorts. Each cohort will consist of 8 subjects. In Cohorts 1 and 3, six subjects will receive LY3478045 and 2 subjects will receive placebo. In Cohorts 2 and 4, six subjects will receive LY3478045 followed by a single dose of atorvastatin 4 hours later and 2 subjects will receive placebo followed by a single dose of atorvastatin 4 hours later.

The maximum dose in males and females in the MAD will be determined based on the PK analyses from previous cohorts, to ensure that the predicted mean exposure at steady state (AUC₀₋₂₄) at the maximum dose in males does not exceed CCI

CCI

A sentinel dosing strategy will be utilized in the cohorts for which the mean AUC₀₋₂₄ is predicted to exceed CCI. Two subjects (1 LY3478045 and 1 placebo) in the cohorts for which the mean AUC₀₋₂₄ is predicted to exceed CCI will receive a sentinel dose on the same day. At least 48 hours after dose, the remaining subjects in each cohort may be dosed based on the available safety data.

Figure GZKA.2 illustrates the study design.

Abbreviations: AT = atorvastatin; LY = LY3478045; PL = placebo.

Figure GZKA.2. Illustration of study design for Part B.

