5.5. Justification for Dose

A planned dose range of 20 to 320 mg was selected to assess safety, tolerability, PK, and PD of LY3478045 following SAD and MAD in healthy subjects:

The planned starting dose in Part A (SAD) is 20 mg in both male and female subjects. The planned top dose in Part A (SAD) is a dose that is predicted to not exceed the mean exposure **CCI** (it is currently anticipated that this dose is 320 mg; however, the exact dose will be determined once PK data are analyzed from the previous cohorts in Part A).

The human PK in healthy subjects was projected with physiologically based pharmacokinetic (PBPK) modeling using data from in vitro studies in human systems. **CCI**

The predicted efficacious dose is 100 to 200 mg once daily based on maintaining plasma exposure over the total cell-based KHK half maximal inhibitory concentration for 24 hours. The PD measurement of serum fructose in Part A (SAD) will define the level of target engagement at each dose, which will further allow refinement of predicted efficacious dose.

The starting dose of **CCI**

[REDACTED]

The dose levels in MAD (Part B) will be selected based on available PK/PD data from Part A. The maximum dose in males in the MAD will be determined based on the PK analyses from previous cohorts to ensure that the predicted mean exposure AUC0-24 at the maximum dose in males does not **CCI**. This is 1/10th of the mean exposure level observed at 75 mg/kg in dogs, which is the lowest dose tested in dogs with no testicular findings. The maximum dose in females in the MAD will be determined based on the PK analyses from previous cohorts to ensure that the predicted mean exposure AUC0-24 at the maximum dose in females does not exceed **CCI**. This is 1/12th of NOAEL exposure at **CCI** dose in dogs.

Table GZKA.2.

CCI

CCI

CCI

6. Study Population

Eligibility of subjects for the study will be based on the results of screening medical history, physical examination, vital signs, clinical laboratory tests, and ECG.

The nature of any conditions present at the time of the physical examination and any preexisting conditions will be documented.

Screening may occur up to 28 days prior to day of clinical research unit (CRU) admission. Subjects who are not enrolled within 28 days of screening may be subjected to an additional medical assessment and/or clinical measurements to confirm their eligibility.

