7.4.1. Dose Decision/Escalation

For dose escalation decisions in Part A and Part B, the following must occur:

- All planned subjects in current cohort must have been dosed.

- Clinical assessment through Day 7 for at least 6 of 8 subjects.
- Safety laboratory tests are obtained from Day 7 for at least 6 of 8 subjects.

For Cohorts 3, 4, and 5 in Part A, the PK results (C_{max} , AUC_{0-inf} , $AUC_{0-tlast}$, and apparent clearance of drug [CL/F]) estimated from the previous cohorts will also be used as supporting data for dose escalation. For Cohort 2 in Part A, PK results may be used if available at the time of dose escalation decision.

In Part A, male and female subjects will only be dosed up to the dose with predicted mean exposure not exceeding CCI [REDACTED]. For Part B, the PK results (C_{max} , AUC_{0-24} , and apparent clearance of drug [CL/F]) estimated from the previous cohorts will also be used as supporting data for dose escalation.

Male subjects are allowed in Part B in the cohorts for which the predicted mean exposure AUC_{0-24} levels for the dose will not exceed CCI [REDACTED] 1/10th exposure level observed at CCI [REDACTED] in dogs, which is the lowest dose tested in dogs with no testicular findings, as determined from PK data in Parts A and B.

Female subjects are allowed in Part B in every cohort. The predicted mean exposure AUC_{0-24} levels for the doses investigated in Part B will not exceed CCI [REDACTED], 1/12th exposure level observed at CCI [REDACTED] in dogs, as determined from PK data in Parts A and B.

More details about the planned dose levels in Parts A and B are available in Section 5.5.

If any of the following scenarios occur, dosing at the current level and further dose escalation will be interrupted until a further sponsor decision:

- 1) One or more subjects on active drug experience an SAE considered to be related to LY3478045.
- 2) One or more subjects on active drug experience 2 clinically significant events defined as moderate to severe symptoms, clinical signs, and clinical laboratory findings that could cause harm to health. The clinically significant events will be determined by the investigator or Lilly CP and may include findings that do not fulfill the criteria for SAEs.

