Appendix 2 lists the laboratory tests that will be performed for this study.

Appendix 5 provides a summary of the maximum number and volume of invasive samples, for all sampling, during the study.

Unless otherwise stated in the subsequent subsections, all samples collected for specified laboratory tests will be destroyed within 60 days of receipt of confirmed test results. Certain samples may be retained for a longer period, if necessary, to comply with applicable laws, regulations, or laboratory certification standards.

The specifications in this protocol for the timings of safety, PK, and PD sampling are given as targets to be achieved within reasonable limits. Modifications may be made to the time points based upon the safety and PK information obtained. The scheduled time points may be subject to minor alterations; however, the actual time must be correctly recorded in the electronic case report form (eCRF). Failure to obtain samples due to clinical issues, such as problems with venous access, technical difficulty with obtaining samples, or if the subject does not show up for planned procedural visits will not be considered a protocol deviation. However, the CRU will still be required to notify the sponsor in writing to account for missing samples to facilitate data reconciliation.

If the predicted mean exposure for the dose at any cohort is estimated to be higher than 71.7 $\mu\text{g}\cdot\text{hr}/\text{mL}$, only female subjects will be included in the cohort and mandated to stay in the CRU until 24 hours after the last dose.

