9.4.5.2. Testicular safety

Male subjects will be enrolled in this trial only if they agree to comply with the contraception requirements specified in this protocol.

In Part B (MAD), blood samples for evaluating hormonal biomarkers of testicular injury (serum concentrations of total testosterone, follicle-stimulating hormone, and luteinizing hormone) will be collected at the visits and times specified in the Schedule of Activities (Section 2).

To mitigate risks of testicular injury, in Part B of the study (MAD), male participants' dose will be restricted to the dose with predicted mean exposure not exceeding **CCI** **CCI** which is the lowest dose tested in dogs with no testicular findings.

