9.6. Pharmacodynamics

Fructose Tolerance Test: Three meals (breakfast, lunch, and dinner) will be served at approximately 20 minutes, 6 hours, and 12 hours after dose with low fructose content. A beverage containing mixture of fructose and glucose CCI in approximately 300 to 500 mL of non-caloric solution will be served with each of the 3 meals on Day 1 in Part A (SAD) and Days 1 and 14 in Part B (MAD). The beverage should be served after a portion of the meal has been consumed. The meals should start at the defined time (20 minutes, 6 hours, and 12 hours postdose) Blood samples for the analysis of fructose will be collected into appropriately labeled tubes containing ethylene diamine tetra acetic acid at the time points specified in the Schedule of Activities (Section 2). Sample handling and shipment to the central laboratory will occur per instructions given to the study site.

The samples will be stored for up to a maximum of 1 year after the last subject visit for the study at a facility selected by the sponsor.

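### In Part B completers the only on-treatment testosterone, FSH and LH value follows dose 1, so the panel cannot show a change that arises under doses 2 to 14 and resolves by Day 28

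*Protocol*

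**What the plan says.** Protocol 9.4.5.2 (Testicular safety) names total testosterone, FSH and LH as the hormonal markers of testicular injury in Part B and leaves their timing to the Schedule of Activities.

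The hormone row is the same in Protocol 2.2 (Cohorts 1 and 3) and 2.3 (Cohorts 2 and 4). It is marked at screening, Day 1 (P, predose), Day 2 (P), Day 28 and early discontinuation, and is empty for Days 3 to 17. The comment in 2.2 asks for samples "collected early in the morning on Days 1 and 2, at the same time for both days, before or immediately after breakfast". The comment in 2.3 agrees: "Samples will be collected early in the morning on Days 1 and 2, at the same time for both days".

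Dosing is once daily for 14 days (5.1.2). The maximum dose for males is chosen "to ensure that the predicted mean exposure at steady state" stays under a redacted limit. Section 5.5 describes that limit as "1/10th of the mean exposure level observed at 75 mg/kg in dogs, which is the lowest dose tested in dogs with no testicular findings". Section 7.4.1 applies it cohort by cohort: "Male subjects are allowed in Part B in the cohorts for which the predicted mean exposure" stays below it.

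Appendix 5 budgets four hormone samples of 3.5 mL in each Part B table. Appendix 2 sends male FSH timing back to the schedule. SAP 9.6.9 describes how the values are listed and adds no time point.

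**The concern.** Part B exists to study repeated dosing, and the male cap is framed in terms of steady-state exposure. The one hormone value taken during dosing is nevertheless a single-dose value. Other safety and metabolic measures are repeated late in dosing: clinical laboratory tests on Days 4, 7 and 14, serum creatinine on Days 7 and 14, and triplicate ECG, fasting insulin and adiponectin on Day 14. The hormone panel is not.

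What is at stake is the wording of the safety conclusion. Normal values on Days 2 and 28 would not support a statement that hormones were unchanged late in a 14-day course. They would show no change about a day after the first dose and none two weeks after the last.

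**Working it through.** 1. **Reproduce the plan's count.** A completer has no early-discontinuation draw, so the marked cells are screening, Day 1, Day 2 and Day 28, which makes 4 samples. 4 x 3.5 mL = 14 mL, the figure in both Part B tables of Appendix 5. Screening might instead be counted under the screening tests, with early discontinuation as the fourth sample. The schedule has no Day 7 or Day 14 hormone cell on either reading.

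2. **Doses given before each draw in a completer** (one dose each morning, Days 1 to 14):
   - Screening: 0
   - Day 1 predose: 0
   - Day 2 predose: 1
   - Day 28: 14, with 28 - 14 = 14 days off drug

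   On-treatment values: 1, after 1 of 14 doses.

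3. **Gap after dosing starts.** Day 2 to Day 28 is 28 - 2 = 26 days. Of these, 14 - 2 = 12 days run up to the last dose and 14 days follow it.

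4. **With a Day 14 predose draw.** This value follows 13 of 14 doses. The gaps become 14 - 2 = 12 days and 28 - 14 = 14 days.

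5. **Treated males.** The sex mix is not given, so this is a range that assumes 6 subjects on LY3478045 per cohort. Protocol 5.4 ties Part B sentinel dosing to cohorts of female subjects at the higher predicted exposures, and SAP 5.2 places sentinel dosing in Cohorts 3 and 4. Together they suggest that males enter Cohorts 1 and 2 only: 0 to 2 x 6 = 12 treated males.

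6. **Blood volume, taking Appendix 5 as it stands.** The hormone row goes from 4 to 5 samples: 5 x 3.5 = 17.5 mL. If the tube were drawn in everyone, the totals would be 355.5 + 3.5 = 359.0 mL (Cohorts 1 and 3) and 448.5 + 3.5 = 452.0 mL (Cohorts 2 and 4). The listed totals include a 3.5 mL serum pregnancy test, assumed not to be drawn in males. A male's totals would then be 355.5 - 3.5 + 3.5 = 355.5 mL and 448.5 - 3.5 + 3.5 = 448.5 mL, so the listed totals are not exceeded.

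7. **Cells against comment.** The cells say predose, but the comment also allows a draw immediately after breakfast. Protocol 9.6 starts the Day 1 breakfast about 20 minutes after the dose. A predose draw, before breakfast, satisfies both the cell and the comment.

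**The case against.** The best case for leaving the schedule alone is that nothing is contradicted and the blind spot is narrow. It covers only a change that appears after dose 1 and is gone within 14 days of the last dose. Day 28 can show a persistent or late change. A subject who stops early has the early-discontinuation draw. Males are also protected by the exposure cap, and the schedule footnotes allow further follow-up visits if safety or PK data call for them. The nonclinical data that might explain the choice of days are redacted. All of this stands, and it keeps the point modest. It does not fill the gap: Protocol 9 says "Modifications may be made to the time points based upon the safety and PK information obtained", which permits an extra draw without planning one.

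The choice of Day 14 can also be challenged. Escalation under 7.4.1 needs clinical assessment and safety laboratory tests through Day 7, so a Day 14 value arrives after that minimum. Day 7 also has predose blood in both schedules, but a value there follows only 6 doses and leaves 28 - 7 = 21 days to Day 28. Day 14 serves the repeat-dose safety conclusion better. It does less for escalation, and that should be said plainly.

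A reader might go further than the documents allow in three ways:

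- **That the schedule breaks 9.4.5.2.** It does not, because that section defers to the schedule.
- **That the Day 1 baseline is really postdose.** The cells say predose and 6.3.1 requires an 8-hour fast before predose blood sampling. Only the comment is loose.
- **That up to 4 x 6 = 24 treated males are affected.** Protocol 5.4 and SAP 5.2, read together, point to Cohorts 3 and 4 being female.

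**Conclusion.** The point holds as a design limitation of modest size, and it is worth correcting because correction is cheap. In a Part B completer the panel observes hormones on treatment once, after 1 of 14 doses, and next when the subject has been off drug for 14 days. It cannot speak to a change confined to the period in between.

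This rests on the schedule columns as extracted from the PDF, which agree with the comment cells and with the four samples in Appendix 5. The estimate of about 0 to 12 treated males assumes six treated subjects per cohort and female-only Cohorts 3 and 4. The second assumption is an inference, since male entry is formally set by predicted exposure.

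A reader might infer that testicular injury would go undetected or that males are unprotected. The documents do not support that: the cap, Day 28 and the early-discontinuation draw remain, and how likely a transient change is cannot be judged from the public text.

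**What to change.** In Protocol 2.2 and 2.3, add the testosterone, FSH and LH tube for males, in both treatment arms, to the Day 14 predose draw, at the same clock time as on Day 1. Extend the comment cell to Day 14 and, in the same edit, align its breakfast wording with the cells marked P. Update the Appendix 5 hormone row in both Part B tables to five samples (17.5 mL), with a note that the fifth is for males.

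The cost is 3.5 mL of blood per male and a protocol amendment to the schedules. No extra venipuncture is needed, because predose blood is already drawn on Day 14 for PK and for fasting insulin and adiponectin.

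The added value would show hormone status after 13 doses. It would not cover doses 2 to 14 throughout, and the report should say so.

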2.3. Part B (Cohorts 2 and 4; Multiple-Ascending Doses)

Procedure	Screening ≤28 days before Day -3	Days												FU ^a	ED ^b	Comments
		-3	-2	-1	1	2	3 to 6	7	8	9 to 13	14	15, 16, 17				
Informed Consent	X															
Admission to CRU ^c		X														
Discharge from CRU													Day 17			
LY3478045 Administration							X									
Medical History	X														Information regarding occasional use of vitamin/mineral supplements will be taken as a part of the medical history evaluation at the time of subject screening.	
Complete Physical Examination	X													X	X	Targeted PE may be conducted at other visits at the discretion of the investigator.
Height	X															
Weight	X	X											Day 15	X	X	
Pregnancy Test	X	X												X	X	Serum pregnancy test will be performed at screening and urine pregnancy test will be performed at all other specified timepoints.
Blood Pressure and Pulse Rate (Supine) ^c	X			X	P, every 1 h up to 12 h postdose	24, 36 h	48, 72 h						X		X	
Body Temperature	X			X										X	X	
Clinical Laboratory Tests (See Appendix 2)	X	X			P		Day 4	X					X		X	
Total Testosterone, Follicle-Stimulating Hormone, and Luteinizing Hormone	X				P	P								X	X	Samples will be collected early in the morning on Days 1 and 2, at the same time for both days, before or immediately

	Screening	Days											FU ^a	ED ^b	Comments
Procedure	≤28 days before Day -3	-3	-2	-1	1	2	3 to 6	7	8	9 to 13	14	15, 16, 17	28		
															after breakfast.
Serum Creatinine					X			X			X				
Single 12-Lead ECG	X											X	X		
TriPLICATE 12-Lead ECG					Predose: 1.5 h, 1 h, and 30 min.						P, 0.5, 1.5, 2.5, 4, 6, 8, 12, 16 h	24 h			
Adverse Event Recording	X	X	X	X	X	X	X	X	X	X	X	X	X		
Pharmacokinetic Sampling ^d					P, 0.75, 1.5, 3, 4, 6, 8, 12, 16 h	24 h (predose)		P, 0.75, 1.5, 3, 4, 6, 8, 12, 16 h	24 h (predose)		P, 0.75, 1.5, 3, 4, 6, 8, 12, 16 h	24, 48, 72 h		Sampling times may be adjusted based upon review of interim PK	
Fasting insulin and Adiponectin					P						P				
Meal (Low Fructose)			breakfast		20 min, 6, 12 h			20 min			20 min, 6, 12 h				
Fructose Beverage (for Fructose Tolerance Test)					during meal: 20 min, 6, 12 h						during meal: 20 min, 6, 12 h				
Fructose Tolerance Test Assay ^d					CCl	24 h (predose and premeal)					CCl	CCl			
CCl				X				X							Atorvastatin will be administered 4 hours after LY3478045 administration on Day 7 or 4 hours after breakfast on Day -2.
CCl				P, 0.5, 1, 2, 3, 4, 6, 20, 32 h	48 h			P, 0.5, 1, 2, 3, 4, 20, 32 h	48 h						Sampling times are relative to the time of
Pharmacokinetics															

Procedure	Screening ≤28 days before Day -3	Days											FU ^a	ED ^b	Comments
		-3	-2	-1	1	2	3 to 6	7	8	9 to 13	14	15, 16, 17			
			8, 12 h					6, 8, 12 h							atorvastatin administration
Genetic Sample				P											
Fasting Biomarker Samples (Nonpharmacogenetic)				X		X						Day 15			
CCI			P, 1.5, 3, 4, 6, 8, 12, 16 h	24 h (predose)	P, 1.5, 3, 4, 6, 8, 12, 16 h	24 h (predose)		P, 1.5, 3, 4, 6, 8, 12, 16 h	24 h (predose)						Sampling times may be adjusted based upon review of preliminary data

Abbreviations: CRU = clinical research unit; ECG = electrocardiogram; ED = early discontinuation; FU = follow-up; h = hour(s); min = minutes; P = predose; PE = physical examination; PK = pharmacokinetics.

Notes: if multiple procedures take place at the same time point, the following order of the procedures should be used: ECG, vital signs, and venipuncture. Samples collected for clinical laboratory tests including urine analysis may be analyzed at a local laboratory. All time points specified in the table are approximate and may be adjusted at the discretion of the investigator.

- ^a Additional FU visits may occur depending upon emerging pharmacokinetic and/or safety data.
- ^b At the discretion of the investigator, subjects may be requested to return to the CRU for safety monitoring at additional visits following completion of the ED procedures. At the discretion of the investigator, assessments may include, but will not be limited to, those presented for the FU visit with the addition of safety laboratory tests.
- ^c Where possible, measurements of blood pressure and pulse rate should be performed at approximately the same time of day at each scheduled time point. Time points may be added for each study period, if warranted and agreed upon between Lilly and the investigator.
- ^d Sampling times are relative to the time of study treatment administration (0 min). Time of breakfast represents 0 min on study Day -2.
- ^e If the predicted mean exposure for the dose at any cohort is estimated to be higher than 71.7 µg·hr/mL, only female subjects will be included in the cohort and mandated to stay in the CRU until 24 hours after the last dose.

3. Introduction

